- c. **Patient Navigation (PN):** phone call from a community health worker to help address hesitancy and access barriers, and to offer at-home rapid test kits. Two types of PN will be tested: **Request PN** (RPN) will contact only those patients who reply YES to a TM/CA message. No PN will have no contact from a patient navigator.

Prior to randomization, patients will be triaged into one of two studies based on self-reported ownership of a smart phone with internet access.

The primary outcome, Testing, captures whether patients actually test with the mailed at-home test kit.

Secondary outcomes include: *Time-To-Vaccine* (time-to-event outcome) as well as several implementation outcomes including *Reach-Engage Testing* (proportion of patients that reply to an offer to receive an at-home rapid test kit) and *Reach-Accept Testing* (proportion of patients that accept an offer to receive an at-home test kit). A similar set of implementation outcomes will be measured for vaccination (i.e., *Reach-Engage Vaccine* and *Reach-Accept Vaccine*).

8. Background and Introduction:

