In RPN patient navigators will assist patients address barriers in engaging in COVID-19 testing and/or vaccination.

Population Health Management Interventions:

SCALE-UP Utah II will build on the standing partnerships among the University of Utah Clinical and Translational Science Institute, Association for Utah Community Health (AUCH), Community Health Centers across the state, and the Utah Department of Health (UDOH); and will leverage infrastructure enabled in SCALE UP Utah I. Hence, we have agile infrastructure, collaborations, and processes that are "shovel ready" to support novel, practical and scalable PHM interventions to increase COVID-19 testing and vaccination among Utah CHC patients.

The study team's primary outcome, Testing, captures whether patients complete at-home tests that were requested through the study.

The secondary outcomes, Time-To-Vaccine (time-to-event outcome) as well as several implementation outcomes including Reach-Engage Testing (proportion of patients that reply to an offer to receive an at-home rapid test kit) and Reach-Accept Testing (proportion of patients that accept an offer to receive an at-home test kit). A similar set of implementation outcomes will be measured for vaccination (i.e., Reach-Engage Vaccine and Reach-Accept Vaccine).

This experimental aims are:

- a. Conducting a 2 (TM vs. CA) X 2 (No PN vs. RPN) factorial design assessing intervention effects on testing outcome. The study team hypothesizes a main effect for CA being more effective than TM Only, and a main effect for PN, comparing RPN vs. No PN (RPN > No PN).
- b. Conducting a 2 arm (No PN vs. RPN) trial among a subset of participants who receive only text messaging (no chatbot). The study team hypothesizes a main effect for PN, comparing RPN vs. No PN (RPN > No PN).
- c. Examining factors associated with at-home testing and/or vaccination uptake over the life of the study. The study team will assess predictors of outcomes and moderators of intervention effects, such as characteristics of patients and contextual factors related to the status of the pandemic.

Text Message Only Study

Overview:

The Text Message Only Study is comprised of participants who either do not answer the original screener question regarding smart phone use or answer that they do not use a smart phone.

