Throughout the course of the study, on a quarterly basis, the study team will send identifiable patient data and study outcomes to project's sponsor, The National Institutes of Health. The identifiable information being transferred will include the CDE portion of the survey. This process will be detailed and approved through data transfer agreements involving the community health centers, the Association for Utah Community Health, The University of Utah Office of Sponsored Projects, The University of Utah IRB, and Duke University, which is housing the data for the National Institutes of Health.

● Yes ○ No		• .		·	ŕ	
If no list the n	rocedures that are n	erformed for res	search nurnoses onl	v (non-standard o	r non-stand	1:

7. Are all procedures for research purposes only (non-standard or non-standard of care procedures)?

If no, list the procedures that are performed for research purposes only (non-standard or non-standard of care procedures):

8. Is there a safety monitoring plan for this study?

Yes No

9. Provide a summary of the statistical methods, data analysis, or data interpretation planned for this study. Factors for determining the proposed sample size (e.g., power) should be stated.

We will conduct two randomized clinical trials: RCT 1 includes participants who affirm they have a smart phone and RCT 2 includes all other participants. We will perform two categories of statistical analyses: 1) Comparing the main effects of TM vs. CA (RCT 1), main effects of RPN vs. no PN (RCT 1 and 2 combined), interaction effects (RCT 1), and follow-up pairwise comparisons of the study arms (RCT 1 and 2); and 2) Evaluating predictors of outcomes and moderators of intervention effects (RCT 1 and 2).

Primary Analyses of Testing for TM vs. CA and no PN vs. RPN. Alpha will be set at 0.0167 to maintain a family-wise error rate of 0.05 across the three primary hypotheses comparing treatment arms. We will apply generalized estimating equations to implement a repeated measures logistic regression to relate the probability of receiving a COVID-19 test within a shorter time frame to the randomized treatment group. Robust sandwich variance estimates will be utilized to account for dependencies between potential repeated observations on each subject (i.e. several potential time-intervals post-randomization where patients might test).

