Predictors of outcomes and moderators of intervention effects. Multilevel generalized linear mixed models will investigate the association between patient, provider, and CHC/clinic level predictor variables with implementation outcomes for each intervention. We will test for patient characteristics and contextual pandemic factors as outcome moderators by fitting an interaction term of each moderator by intervention.

Statistical Power. The participating CHCs have 43,325 patients with a clinical encounter in the past three years. In SCALE-UP Utah, 15% of patients have opted out of receiving text messages and will not be included in SCALE UP II. Based on data from SCALE-UP Utah and prior research, we anticipate ~20% opt outs, leaving a total of ~29,500

patients for randomization to the six study arms. We have satisfactory power for detecting feasible CA vs TM; and RPN vs No PN differences on our primary outcome of *Recurrent-Testing*.

IRB_00150669

Created: 1/10/2022 7:14 AM IRB_00150669

- Request for Waiver of Consent

PI: [name] [name]

Submitted: 3/21/2022

Title: SCALE UP Utah II: Community-Academic Partnership to Address COVID-19 Testing and Vaccination Among Utah Community Health Centers

Request for Waiver or Alteration of Consent -

	Date Created	Type of Request	Purpose of Waiver Request
View	2/25/2022	Waiver of Informed Consent	The purpose of this waiver is to review EHR patient data at participating CHCs and linked USIIS vaccination data, using that data to establish cohort selection for research intervention and randomizing selected patients to research interventions without the patient's consent.
View	2/25/2022	Waiver of Informed Consent	The purpose of this waiver is for the use of EHR and USIIS data post-intervention implementation to analyze which patients, randomized to each intervention, were ultimately tested and/or vaccinated for COVID-19.

PI: [name] [name] Submitted: 3/21/2022

Title: SCALE UP Utah II: Community-Academic Partnership to Address COVID-19 Testing and Vaccination Among Utah Community

Health Centers

Request for Waiver or Alteration of Consent

1. Purpose of the Waiver Request:

The purpose of this waiver is to review EHR patient data at participating CHCs and linked USIIS vaccination data, using that data to establish cohort selection for research intervention, and randomizing selected patients to research interventions without the patient's consent.

2. Type of Request:

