## SCALE-UP Utah II: Community-Academic Partnership to Address COVID-19 Text

Messaging Study

9/5/2024

NCT05533918

The primary hypotheses for the Smartphone study were main effects for delivery mechanism (Chatbot > TM), main effects for PN (PN > No PN), and main effects for message frequency (10-day > 30-day). For the non-Smartphone study, the primary hypotheses were main effects for PN (PN > No PN) and main effects for message frequency (10-day > 30-day). These hypotheses were adjusted for multiple comparisons using the Bonferroni method at an alpha of .0167 for the Smartphone study to account for three coprimary comparisons, and .0250 for the non-Smartphone study to account for two coprimary comparisons.

Separate analyses were conducted for the Smartphone study and the non-Smartphone study. Log-binomial models were used to regress *Reach-Accept Testing* upon each of the three main effects in the Smartphone study, i.e. Chatbot (vs. TM), PN (vs. No PN), and outreach frequency (10 vs. 30 days); and two main effects in the non-Smartphone study, i.e. PN (vs. No PN) and outreach frequency (10 vs. 30 days). The log-binomial models included covariates to adjust for randomization stratification variables (rural vs. urban, CHC, randomization arm in our previous SCALE-UP I trial) and a categorical variable reflecting the calendar month when the participant received the first intervention message. Adjusted risk ratios (aRR) and confidence intervals were reported for each main effect. In preliminary analyses reported in the Online Supplement, the pairwise and 3-way interactions between the main effects were added to the log-binomial models described

above in order to assess for any effect modifications across interventions, but these analyses did not support the inclusion of the interactions.

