We preliminarily estimated a model specification including the pairwise and 3-way interactions between the main effects and the smartphone ownership indicator in order to assess for any synergistic and/or antagonistic effect modifications across interventions. We have conducted these analyses for the primary outcome (Reach-Accept Testing) for both the smartphone and non-smartphone groups. In both analyses, the estimated coefficients on all interaction terms were not statistically significant at the 5% level. We have conducted an omnibus test (using the car::linearHypothesis function in R) and found that in each case, these coefficients were jointly not statistically significant.

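### The SAP makes accepting a test kit the primary outcome, while the protocol's primary is using the kit, and the change is neither stated nor dated

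*SAP*

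**What the plan says.** **Protocol.** Under Study Purposes and Objectives: "The primary outcome, Testing, captures whether patients actually test with the mailed at-home test kit". Section 4 (Study Information), question 6, agrees: "The study team's primary outcome, Testing, captures whether patients complete at-home tests that were requested through the study". Both places put acceptance among the secondary implementation outcomes, defined as "Reach-Accept Testing (proportion of patients that accept an offer to receive an at-home test kit". In question 9 the primary model is a repeated-measures logistic GEE, meant to "relate the probability of receiving a COVID-19 test within a shorter time frame to the randomized treatment group". The navigation contrast is planned as "main effects of RPN vs. no PN (RCT 1 and 2 combined". The power paragraph uses a third label, Recurrent-Testing, for the primary outcome.

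**SAP (dated 9/5/2024, written in the past tense).** "Log-binomial models were used to regress *Reach-Accept Testing* upon each of the three main effects in the Smartphone study", with matching two-factor models in the non-Smartphone study. The final paragraph, on interactions, calls Reach-Accept Testing the primary outcome: "We have conducted these analyses for the primary outcome (Reach-Accept Testing) for both the smartphone and non-smartphone groups". It reports that the interaction tests were not significant. Testing and Recurrent-Testing do not appear in the SAP.

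**The concern.** Accepting a kit comes before using it. An effect on acceptance does not show that more people tested, which is the protocol's primary question. Patient navigation and the conversational agent are meant to work on hesitancy and barriers, so the share of acceptors who go on to use the kit could differ by arm, in either direction.

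Timing is the second issue. The SAP already contains results. Without a dated record, a reader cannot tell whether acceptance was made primary before or after outcome data were available. The Bonferroni thresholds in the SAP (.0167 and .0250) cover the comparisons within each study on the outcome analysed. They do nothing about a choice between outcomes.

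**Working it through.** **1. The plan's own figures.** The alphas reproduce: 0.05/3 = 0.0167 and 0.05/2 = 0.0250. So does the number for randomisation: 43,325 × 0.85 × 0.80 = 29,461, against about 29,500 in the power paragraph. That paragraph gives no rate, effect size or power value, so no power figure can be checked for any outcome.

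**2. Which outcome is primary, place by place.**

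| Place | Primary outcome |
|---|---|
| Protocol, Study Purposes and Objectives | Testing: kit actually used |
| Protocol, section 4, question 6 | Testing: requested at-home test completed |
| Protocol, section 4, question 9, primary analyses | Receiving a COVID-19 test, repeated measures |
| Protocol, section 4, question 9, power | Recurrent-Testing |
| SAP, primary models and final paragraph | Reach-Accept Testing: kit accepted |

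The protocol's labels are not uniform, but all of them concern testing. None is acceptance.

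**3. Do the amendments explain it?** The forms submitted 11/2/2022, 1/18/2023 and 6/6/2023 list no change of primary outcome. The last one names the statistical plan as affected, but its only design change is the enrolment goal of 43,325. That number stands in the power text next to Recurrent-Testing. The protocol text shown therefore includes that amendment and still names a testing outcome.

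**4. What could differ between the two outcomes.** All rates below are assumed, because the documents give none. Over all randomised patients, P(Testing) = P(accept) × P(use given acceptance), so

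Testing RR = acceptance RR × (use among acceptors, intervention ÷ control).

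- Break-even use ratio = 1/RR. For acceptance RRs of 1.1, 1.2, 1.5 and 2.0 this is 0.91, 0.83, 0.67 and 0.50.
- At an acceptance RR of 1.2: 1.2 × 0.80 = 0.96 and 1.2 × 1.25 = 1.50.

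**5. How much survey response a Testing analysis would need.** Let r be response and u observed use, both equal in the two arms. In the worst case every intervention non-responder is a non-user and every control non-responder a user:

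lower bound = RR·u·r / (u·r + 1 − r), which exceeds 1 when r > 1/(1 + u(RR − 1)).

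- RR 1.2: 1/1.13 = 88.5% at u = 0.65; 86.2% at u = 0.80; 90.9% at u = 0.50.
- RR 1.5: 1/1.325 = 75.5% at u = 0.65; 71.4% at u = 0.80; 80.0% at u = 0.50.

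These thresholds ignore sampling error.

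**6. Precision.** With acceptance a and responses missing at random within arm, the SE of the log Testing RR relative to that for acceptance is √(1 + (1 − u)/(u·r·(1 − a))).

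- a = 0.10, u = 0.65: √(1 + 0.35/0.585) = 1.26 at r = 1, and 1.48 at r = 0.5.
- Over a of 0.05 to 0.30 and u of 0.50 to 0.80: 1.12 to 1.56 at r = 1, and 1.24 to 1.96 at r = 0.5.

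**The case against.** The strongest reply is that only non-disclosure in these pages is shown.

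- **A record may exist elsewhere.** The SAP is short, cites an online supplement and carries a registry number. This stands, and supplying that record is the first part of the fix.
- **The protocol evidence is soft.** The study description on each amendment form is filled in from the application, and the application was only partly updated: section 4 still mentions three navigation conditions, and the waiver requests still cite about 118,000 patients. This weakens the inference, but only in part. The description did change between the first two forms, from proactive and reactive navigation to request navigation, and kept Testing as primary.
- **Acceptance may be the practical choice.** Kit requesters need not share results with their clinic, and the state immunisation system is described as a source of vaccination records, so those sources may not capture kit use. The clinic record may instead serve for in-clinic tests, with the survey covering kits. That is plausible. But the protocol plans the survey to measure test use, and the January 2023 form says it was added to assess outcomes. If feasibility drove the change, the SAP should say so.
- **The SAP claims nothing about kit use, and the bounds may be wide.** Both are fair. Limiting the conclusion is a safeguard for reporting. The response thresholds above show that worst-case bounds may well include no effect, which is itself worth knowing.
- **A survey-based kit-use table would not restore the planned repeated-measures analysis.** Correct, so it has to be labelled as additional.

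**Conclusion.** The point holds and must be fixed; the SAP is wrong as written. This rests on the text alone: kit use is primary in the protocol, acceptance is secondary there, and the SAP promotes acceptance without saying so. The documents do not show that the choice followed sight of results, and they do not show that it preceded it.

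The size and direction of any gap between the two effects cannot be derived from the documents. The figures above only show, under assumed rates, that an acceptance RR of 1.2 is compatible with anything from a slightly adverse to a larger effect on Testing.

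**What to change.** 1. **Disclose.** State in the SAP that the primary outcome analysed differs from the protocol's. Give the date and reason, relative to access to outcome data. If no record from before that access exists, say so.
2. **Limit the primary conclusion** to requesting or accepting a kit.
3. **Report Testing by arm** as a labelled additional analysis over all randomised patients in each study. Count non-requesters as not tested with a study kit, take use among requesters from the planned survey, show response by arm, and give best-case and worst-case bounds. State that this departs from the protocol's GEE model and its pooled navigation contrast, and that making Testing primary again now would be post hoc.
4. **Reconcile the supporting text.** The survey clock runs from eligibility in section 4 and in Risks and Benefits, but from the first request in Consent Process, question 3. Section 4 measures test use by survey, while the consent waivers plan to take outcomes from clinic records and, in the second, immunisation data as well.
5. **Annotate, but keep, the power sentence.** It refers to Recurrent-Testing, gives no figures, and does not establish power for acceptance.

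**Cost.** Some SAP wording, one protocol annotation, the reconciliations, and one table from survey data already planned. The Testing estimate will be less precise (SE ratio above) and depends on response. Some patients may be surveyed later than 3 months, because the survey had not started when 26,876 of 43,325 (62%) were reported enrolled. That form was created 3/30/2023 and submitted 6/6/2023, which brackets the count but does not give individual delays. Limiting the conclusion gives up a primary claim about testing.

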- 3. Patient Navigation (PN): phone call from a community health worker to help address hesitancy and access barriers, and to offer at-home rapid test kits. Two types of PN will be tested: Request PN (RPN) will contact only those patients who reply YES to a TM/CA message. No PN will have no contact from a patient navigator.

Prior to randomization, patients will be triaged into one of two studies based on self-reported ownership of a smart phone with internet access.

The primary outcome, Testing, captures whether patients actually test with the mailed at-home test kit.

Secondary outcomes include: Time-To-Vaccine (time-to-event outcome) as well as several implementation outcomes including Reach-Engage Testing (proportion of patients that reply to an offer to receive an at-home rapid test kit) and Reach-Accept Testing (proportion of patients that accept an offer to receive an at-home test kit). A similar set of implementation outcomes will be measured for vaccination (i.e., Reach-Engage Vaccine and Reach-Accept Vaccine).

1. Name of Amendment:

Use a name that will make it easy to identify the contents of the amendment. You may use

information such as the sponsor amendment number or an internal tracking number.

Adding Elite as study site, changing n, adding updated consent docs

2. Type of Amendment (check all that apply):

Administrative changes:

Changes to study design elements:

Changes to consent, parental permission, or assent documents

3. Current Status of the Study:

Open for Enrollment

4. Total Number of Participants Enrolled To Date

At Utah: 26876 All Centers: 26876 IRB_00150669 - AM_Adding Elite as study site, changing n, adding updated consent

docs

Created: 3/30/2023 10:08 AM **AM_00047765**2. Description

PI: [name]

Submitted: 6/6/2023

Title: SCALE UP Utah II: Community-Academic Partnership to Address COVID-19 Testing and Vaccination Among Utah Community

Health Centers

2.	Am	endn	nent	Des	crij	otion
----	----	------	------	-----	------	-------

	_				_			_
Vali	have ir	ndicatod	that the	following	types of	change	are being	ı mada:
IUU	Have II	IUICALEU	uiai iiie	IUIIUWIIIU	LVDES OI	CHAHUES	are bellio	ı ıııauc.

Administrative changes:

Changes to study design elements:

Changes to consent, parental permission, or assent documents

- 1. What changes are being made? List and number each change, grouping similar changes together.
 - 1. Administrative changes. We are adding Elite Research as a study site

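### The supplied SAP was written after by-arm models of its primary outcome had been fitted, so Bonferroni control is not shown for five elements found only there

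*SAP*

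**What the plan says.** The SAP is a short unnumbered text whose only date is 9/5/2024. It shows no version history, sign-off or data-lock date, and its verbs are in the past tense.

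- Error control: "These hypotheses were adjusted for multiple comparisons using the Bonferroni method at an alpha of .0167 for the Smartphone study", for three comparisons, with .0250 for two comparisons in the non-Smartphone study.
- Model: "Log-binomial models were used to regress *Reach-Accept Testing* upon each of the three main effects in the Smartphone study". Covariates are the randomization stratification variables and calendar month of first message.
- Model form: interaction terms were fitted, and "these analyses did not support the inclusion of the interactions".
- Closing paragraph: "We have conducted these analyses for the primary outcome (Reach-Accept Testing) for both the smartphone and non-smartphone groups". It then states that the interaction terms were not significant, singly or jointly.

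The protocol is prospective. Under Study Purposes and Objectives, the primary outcome is Testing (use of the mailed kit), and Reach-Accept Testing is among the secondary outcomes. Section 4, item 9 sets alpha at 0.0167 for three primary hypotheses within one 5% family. It compares RPN with No PN in RCT 1 and 2 combined, and on the model says "We will apply generalized estimating equations to implement a repeated measures logistic regression".

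**The concern.** Bonferroni adjustment controls the family-wise error only for a family, outcome and model settled independently of the results. A text that reports fitted models of its own primary outcome cannot by itself show that this was so. An earlier document could, but the only earlier plan supplied, the protocol's item 9, describes a different analysis.

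At stake is which results may be called confirmatory. A reader of the SAP would take every listed test as a prespecified primary comparison held at 5% per study. For elements that have no dated source before the results, that reading has no documentary support.

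**Working it through.** **1. The SAP's own levels.** 0.05/3 = 0.01667, stated as .0167; 0.05/2 = 0.0250, as stated. The arithmetic is right, so the question is timing.

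**2. Was the text written after by-arm models were fitted?** Yes. The interaction models contain the randomised factors and have the primary outcome as response, and the SAP gives their results. This does not depend on the 9/5/2024 date.

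**3. Which primary elements have a prospective source?**

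| Element | Protocol | SAP |
|---|---|---|
| 0.0167 level, 5% target | Section 4, item 9 | same level |
| CA > TM; RPN > No PN | Section 4, item 6, aim a | same |
| RPN > No PN in the text-only study | Section 4, item 6, aim b | same |
| Stratification covariates | not listed | described as randomization variables, hence set at randomisation |
| Primary outcome | Testing | Reach-Accept Testing |
| Message frequency | a procedure only (Step Four, Implementation) | coprimary: "main effects for message frequency (10-day > 30-day") |
| Model | GEE repeated-measures logistic | log-binomial |
| Calendar month | absent | covariate |
| Families | one of three at 0.05; PN combined over RCT 1 and 2 | two: three at .0167, two at .0250 |

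The first four rows are not in question. The last five are the elements found only in the SAP.

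**4. How the families differ.**
- Protocol: 3 × 0.0167 = 0.0501.
- SAP, Smartphone: 3 × 0.0167 = 0.0501.
- SAP, non-Smartphone: 2 × 0.0250 = 0.0500.
- SAP, both studies: 0.0501 + 0.0500 = 0.1001 over five tests; if independent, 1 − 0.9833³ × 0.975² = 0.0962.

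The protocol's 0.0167 therefore cannot stand as prior authority for the whole SAP scheme. It belongs to a family with different members.

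**5. Illustration of what an unfixed choice could cost.** Assumptions, none from the documents: three independent null hypotheses, two-sided tests at .0167 (critical value 2.393), two candidate outcomes with correlation ρ, and a claim allowed on either outcome.

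Per hypothesis, p(ρ) = 1 − P(|Z₁| < 2.393 and |Z₂| < 2.393). Family-wise error = 1 − (1 − p)³.

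| ρ | p | Family-wise error |
|---|---|---|
| one fixed outcome | 0.0167 | 4.9% |
| 0.9 | 0.0245 | 7.2% |
| 0.8 | 0.0273 | 8.0% |
| 0.7 | 0.0291 | 8.5% |
| 0.5 | 0.0314 | 9.1% |

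This covers choice of outcome only. It puts no figure on the model, the calendar-month covariate, the frequency hypothesis or the second family.

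**The case against.** **Text written late does not show decisions made late.** This stands. The date 9/5/2024 is also the print date on the protocol files, so it may be only an upload date, and an earlier dated plan may exist. A reader might infer that the outcome was switched after results were seen; nothing supplied shows that.

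**Much of the SAP is prospective.** This stands too. A reader might infer that the whole SAP, including its study-by-study analysis, is post hoc. Aim b already states a separate RPN hypothesis for the text-only study, and the 0.0167 level and the CA and RPN hypotheses are in the protocol.

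**Dropping interactions is weak evidence of a results-driven primary analysis.** Largely accepted. Main effects were the protocol's hypotheses, and item 9 already planned interaction tests in RCT 1. The reported interaction results matter here because they show the order of events.

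**The protocol's own statistical text may not predate the data.** The amendment submitted 6/6/2023 lists the statistical plan among affected sections, with enrolment at "At Utah: 26876 All Centers: 26876". Its stated design change is the enrolment goal, and enrolment does not mean that outcomes had been seen. No earlier version of item 9 is supplied, so this cannot be settled either way.

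**The protocol's analysis may not be runnable.** This stands and limits the remedy. Under Patient Surveys and Consent Process, use of tests is assessed by one consented survey at about 3 months, offered to kit requesters and a matched sample of non-requesters. The documents show no interval-level data on kit use for everyone randomised. Item 9 also speaks of three primary hypotheses while naming two treatment main effects.

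**The protocol analysis may have been reported elsewhere.** A reader might infer from the SAP's silence that it was not. A SAP cannot show this, and the Online Supplement that it mentions was not supplied.

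**Conclusion.** The point holds for five elements: Reach-Accept Testing as primary outcome, message frequency as a coprimary hypothesis, the log-binomial model, the calendar-month covariate and the .0250 family. For each, the only supplied source postdates by-arm modelling of the primary outcome, so the claimed Bonferroni control is undocumented. It is not shown to be false.

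The outcome is the weightiest of the five, because the protocol names it as secondary. The 7.2% to 9.1% range rests on assumed correlations and on free selection between two outcomes. It measures what is at risk and is not evidence that selection occurred. The 0.1001 total over both studies should not be read as an error in itself: separate families for two separate trials can be defended, provided that they were set in advance. The data are not invalidated; the status of some claims is open.

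**What to change.** 1. For each of the five elements, cite a dated record showing that it was fixed before anyone saw outcomes by arm.
2. Where no such record exists, label the element post hoc and drop the claim of confirmatory family-wise control for it.
3. Report Testing as the protocol-defined primary outcome with the item 9 contrasts, including the combined RPN versus No PN test, as far as the collected data allow. If that analysis cannot be run, state why.
4. Present the log-binomial Reach-Accept results alongside it, under the status that steps 1 and 2 give them.

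Steps 1 and 2 cost a document search and changes of wording. Step 3 costs more than a rerun if kit use is known only from the survey, because non-response and the matched sampling would then have to be handled. The downside is that some claims become weaker.
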